Plan to use a monophasic waveform having 100microsec pulse rate, at a pulse rate of 35 Hz to voltage that generates twitch contraction or if the research subject can tolerate the voltage needed for a contraction then as high as tolerated. These parameters are taken from clinical trial showing improvement in patients with carpal tunnel (Gordon et al 2009). Electrical stimulation will be produced with the ortho 3 stim which has passes the inspection by the rehabilitation facility for use. The cathode will be placed over the ipsilateral facial muscle to stimulate and the anode behind the ipsilateral ear. All devices are noninvasive without any skin puncture.

Muscles stimulated were:

- 1) Frontalis (FM) to produce brow elevation
- 2) Orbicularis oculi (OOc) to produce eyelid closure
- Zygomaticus major muscle (ZMM) to produce elevation of the oral commissure superiorly and posteriorly
- 4) Orbicularis oris (OOr) to produce lip pursing

Patients are asked to mimic the movements produced by electrical stimulation voluntarily on the nonparalyzed side of the face in front of a mirror during therapy. Electrical stimulation is performed concurrently with facial exercises and mirror therapy. Initially, electrical stimulation is performed with a therapist twice before transitioning to home patient-driven electrical stimulation (duration of first appointment is 40 minutes). Ten contractions of each muscle group will be performed. A hand out will be provided for patients to take home and review the instructions on how to perform home electrical stimulation.

Home electrical stimulation is to be performed for 12 minutes daily (3 mins per muscle). Compliance is defined as performing the electrical stimulation 5 of 7 days of the week.

Duration of therapy: Therapy is to start during the first week of onset of facial paralysis and be used daily for three months or sooner until complete recovery is achieved, as judged by study personnel. The design for electrical stimulation was derived from review of the literature and from focus groups with two physical therapists that treat facial paralysis. OHSU has a physical therapist, [name], who is trained in electrical stimulation of the face and has been providing electrical stimulation for patients being treated at OHSU. [name] will be a collaborator in this trial.

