The physical therapist will meet with patients twice. The first session will be 1 hr and will include evaluation and treatment showing patients how to use the electric stimulation machine. The second session will only be 30 min and will be 1 to 2 weeks after the first session. During the second session the participants will demonstrate how they perform electric stimulation.

Comparison: Subsensory electrical stimulation

The electric stimulation device has a placebo setting that delivers minimal electricity.

The settings will be the same as the intervention, the voltage will be below the earliest point at which patients feel the electricity.

The patient and physical therapist will not be blinded. The rest of the research team will be blinded.

All patients will receive steroids (prednisolone 25mg by mouth twice daily, or an equivalent regimen) and Ramsay Hunt syndrome patients should receive antivirals at standard doses (acyclovir 200mg five times a day) (Sullivan et al. 2007).

Outcome:

Primary outcome: Proportion of patients with complete recovery at one, two, and three months Complete recovery is defined as symmetry at rest and symmetry during movement without evidence of synkinesis.

To evaluate for complete recovery, standardized photos of patients at rest, and during movement, will be evaluated by three treatment-blinded otolaryngologists. Recovery will be measured using the eFACES assessment with is a clinician-graded electronic assessment with high inter-rater reliability.

The photos will be standardized as follows:

- Frontal face photo at rest
- 2) Frontal face photo with strong eyelid closure (which shows midface, chin and neck synkinesis)
- Frontal face photo with strong smile (which shows periocular synkinesis and oral commissure movement)

Secondary outcomes:

- 1) House Brackmann scale scoring will be determined by the three otolaryngologists, reported as an average of their three scores after evaluating the three photos mentioned in the primary outcome.
- 2) Patient reported, facial nerve specific, validated quality of life questionnaires:
 - FaCE scale (Khan et al. 2001) measured facial movement, facial comfort, oral function, eye comfort, lacrimal control, and social function.

- b. Synkinesis Assessment Questionnaire (Mehta et al. 2007)
- Objective measurements of facial symmetry at rest and with facial expression as measured by MEEI FACE-gram program.

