There will be two meetings with physical therapist to learn how to do therapy. Additional follow up happens once a month for 3 months.

The researcher will be conscientious to minimize undue influence.

To ensure understanding, the researcher will explain the project and a copy of the consent will be given to patients.

Non-English Speaking Subjects

Non- English speaking subjects will not be included in the study

6. Procedures Involved

This is a randomized study for electric stimulation. Half of the patients will not receive electric stimulation. All patients will have a total of 6 visits that are detailed below (table). The first visit is a screening. The next two visits are with physical therapist to learn rehabilitation exercises and possibly electric stimulation. The next three visits are three follow up appointments to check on

If chosen to receive electric stimulation, subjects will use electric stimulation at home for 15 min per day until you recover or for 3 months. We will provide the equipment. The FDA approves the use of electric muscle stimulation.

200	322 23			U		1745	257
Visit 1	Visit 2	Visit 3	Visit 4	Visit 5	Visit 6	Phone call	
Day 1	Week 1	Week 2	Month 1	Month 2	Month 3	Month 6	

Consent	X						
Discussion							
Physical		X	X			3	
therapy						(
Photography	X			X	X	X	
Questionnaires	X			X	X	X	X
Total time	1 hour	1 hour	1 hour	30 minutes	30 minutes	30 minutes	20 minutes
Payment	\$50	\$30	\$30	\$50	\$50	\$50	\$0

The quality of life questionnaires we will collect are called the SF-12, FaCE scale and Synkinesis Assessment Questionnaire. These questionnaires ask you about your own quality of life in relation to facial movement and facial spasms. It will take 20 minutes for you to fill both questionnaires. Additional questions about your general health will be asked at the consent and the follow up visits and if you are in the electric stimulation we will ask about tolerability and satisfaction. The FaCE scale, synkinesis assessment questionnaire, the initial screening questionnaire, the follow up questionnaires, and the electric stimulation satisfaction and tolerability forms are all uploaded with this application.

During this study we will obtain facial photographs at various facial expressions. A photo at rest, one with brow elevation, one with eye closure and another one with a smile will be takes. We expect it will take 10 minutes to take the photographs.

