Total participation in the study is 3 months. We will also call you at 6 months for a telephone interview. The 6 month interview form is uploaded in this application as well.

To prevent loss of confidentiality, all of the information and photographs collected will be stored under password protected computer at OHSU and only study personnel will have access to these data. The data will be de-identify as early as possible.

[figure not shown]
If a subject withdraws from electric stimulation intervention, we will continue data collection.

Physical therapy is part of routine Bell's palsy care. Physical therapy would be performed or used even if a subject was not in this study. The costs for these services or items will be billed to your insurance.

Block Randomization for Treatment Assignment

We will use stratified, randomized block design to randomly assign study participants into either treatment or control groups with a 1:1 ratio. Four strata will be utilized based on study participant disease status at enrollment: 1) > 60 years of age with incomplete paralysis, 2) > 60 of age with complete paralysis, 3) complete paralysis (\leq 60 years of age), less than 14 days in duration, and 4) complete paralysis (\leq 60 years of age),P greater than 14 days in duration (*Figure 2*). Study patients providing informed consent, meeting inclusion and exclusion criteria, will be assigned and evaluated in a single-blind fashion (i.e. research staff blinded but the patients and the physical therapist will be unblinded). Due to the relatively small sample size (\sim 20 patients for each treatment) and the number of

strata, we will utilize a minimum block size of 2 within each strata to minimize potential imbalances in treatment assignments. All block assignments will be completed to avoid treatment bias and provide even, but potentially unbalanced, numbers of enrollment subjects per strata.

7. Data and Specimens

a. Handling of Data and Specimens

All data and photos will be stored at OHSU computers under password protection. Only research study members will collect and store information. Only study members will have access to the data for analysis.

b. Sharing of Results with Subjects

Results will not be shared with the subjects

c. Data and Specimen Banking

Data from surveys will be stored using a REDCap database.

8. Data Analysis

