Please note [name], CCRP is a senior research analysis who is a collaborator in this study. We will provide guidance in statistical strategies and perform statistical testing. Results in the group that does receive electric stimulation will be compared to results in the group that did not receive electric stimulation.

Primary outcome: Proportion of patients with complete recovery at one, two, and three months

To evaluate for complete recovery, standardized photographs of patients at rest and during movement will be evaluated by three treatment-blinded otolaryngologists at the conclusion of the study. Recovery will be measured using the eFACES assessment with is a clinician-graded electronic assessment with high inter-rater reliability.

The photos will be standardized as follows: 1) Frontal face photo at rest, 2) frontal face photo with strong eyelid closure (which shows midface, chin and neck synkinesis), 3) frontal face photo with strong smile (which shows periocular synkinesis and oral commissure movement), and 4) brow elevation. The eFACES comes with a training video for the raters to use.

Secondary outcomes:

- 1. House Brackmann scale scoring will be determined by the three otolaryngologists, reported as an average of their three scores after evaluating the three photos mentioned in the primary outcome.
 - a. Wilcox rank sum test will be used to compare House Brackmann results.
- 2. Patient reported, facial nerve specific, validated quality of life questionnaires:
 - a. FaCE scale (Khan et al. 2001) measured facial movement, facial comfort, oral function, eye comfort, lacrimal control, and social function
 - b. Synkinesis Assessment Questionnaire (Mehta et al. 2007)
 - c. Medical Outcomes Study Short Form-12 (SF-12)
- Objective measurements of facial symmetry at rest and with facial expression as measured by MEEI FACE-gram program.
 - a. Reporting palpebral fissure width and corner of the mouth symmetry at rest
 - b. Reporting brow elevation while raising the eyebrow
 - c. Reporting commissure excursion during smile
- 4. Time to complete recovery as judged by researchers (which will be in 1 month intervals)_
- Patient satisfaction and treatment tolerability will be reported at three-month intervals by patients using a Likert scale. Tolerability is rated as: very easily tolerated, easily tolerated, moderately tolerated, hardly tolerated, and not tolerated at all.

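### Time to complete recovery is not tied to the blinded photograph panel that grades recovery for the primary outcome, and the blind of whoever judges it is stated but not protected.

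*Combined protocol and SAP*

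**What the plan says.** **Primary outcome.** Section 8 (Data Analysis) has photographs at rest and in movement "will be evaluated by three treatment-blinded otolaryngologists at the conclusion of the study". The proportion recovered is reported at one, two and three months. Section 4 (Outcome) supplies the only definition: "Complete recovery is defined as symmetry at rest and symmetry during movement without evidence of synkinesis".

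**Time to recovery.** Section 4 lists this secondary outcome without naming an assessor. Section 8, secondary outcome 4, does name one: "Time to complete recovery as judged by researchers (which will be in 1 month intervals".

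**A judgement during the study.** Section 4 (Duration of therapy) has treatment continue for three months or, if sooner, "until complete recovery is achieved, as judged by study personnel".

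**Blinding.** Section 4 (Comparison) states: "The patient and physical therapist will not be blinded. The rest of the research team will be blinded". Section 6 (Block Randomization) repeats it: "research staff blinded but the patients and the physical therapist will be unblinded".

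**What follow-up staff handle.** Section 6 tells the patient that "if you are in the electric stimulation we will ask about tolerability and satisfaction". Section 8 has diaries of use handed in each month.

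**The concern.** The plan measures one concept, complete recovery, through two channels. One is a blinded panel reading photographs after the study. The other is an unnamed group of researchers working in monthly steps. If the channels differ, a patient can count as recovered at month 1 for time to recovery and as not recovered at month 1 for the primary. The plan does not say which result stands.

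The panel is also well shielded from knowledge of the arm, whereas staff who meet patients every month are not. If whoever judges time to recovery learns the arm, expectation can move the recovery month in one group only. The pilot is meant to inform the effect size for a larger trial, so a recovery measure that contradicts the primary, or leans towards one arm, would be carried into that design.

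**Working it through.** No figure in the plan needs reproducing. The check compares the text, followed by an illustration of size.

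**1. Are the assessors the same?** In the Section 8 list of secondary outcomes, item 1 (House Brackmann) refers back to the three otolaryngologists. Item 4, in the same list, says researchers. The change of term makes a different assessor a fair reading, though not a certain one. No section says that item 4 is computed from the panel's grades, and none gives a rule for disagreement.

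**2. Could the panel supply every recovery judgement?** No. Panel members grade at the end of the study, while the judgement in Section 4 that ends therapy early is made during treatment. A second recovery judgement, by other staff, is therefore built into the trial. The plan does not say whether item 4 uses it.

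**3. Is the stated blind protected?** The possible routes are:
- *Patients.* They know their arm (Sections 4 and 6) and return at months 1, 2 and 3.
- *Tolerability and satisfaction questions.* Section 6 puts these only to the stimulation arm, so asking them identifies the arm. Their timing is unclear. Section 6 mentions them together with the follow-up visits; Sections 4 and 8 give three-month intervals. On the three-month schedule they could not affect a judgement at month 1 or 2.
- *Diaries.* They reveal the arm only if controls have no device. Section 6 says half the patients receive no stimulation, and the opening of Section 4 describes the control as standard of care alone. Section 4 (Comparison) instead gives controls subsensory stimulation from the device, in which case a diary alone reveals nothing. These passages conflict.
- *Separation of roles.* No section keeps the staff who collect these items apart from those who judge recovery.

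**4. Size (illustration, on assumptions).**
- Inputs: 15 per arm (Sections 4, 5 and 8) or about 20 (Section 6, Block Randomization).
- One patient called recovered a visit early moves that visit's proportion by 1/15 = 6.7 points, or 1/20 = 5 points. The documents do not say how many patients might be affected.
- A second illustration assumes no true effect, control patients judged as the panel would judge them, and a share b of the active-arm patients not recovered by month 3 being called recovered. With true recovery p, the false difference is d = (1 − p) × b. For p, Section 4 cites 61% (complete paralysis) and one third (over 60). These are background rates, not rates stated for month 3.

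| b (assumed) | d at p = 61% | d at p = 1/3 |
|---|---|---|
| 0.1 | 3.9 points | 6.7 points |
| 0.2 | 7.8 points | 13.3 points |
| 0.3 | 11.7 points | 20.0 points |
| 0.5 | 19.5 points | 33.3 points |

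- At b = 0.2, the chance that at least one of 15 active-arm patients is classed differently from the panel is 1 − (1 − d)^15. This gives 1 − 0.922^15 = 70% and 1 − 0.867^15 = 88%.
- By exact enumeration with 15 per arm, the two-sided 5% false-positive rate of a pooled z test at b = 0.2 rises from 4.9% to 7.5% (p = 61%) and from 5.3% to 11.2% (p = 1/3). With Fisher's exact test it rises from 1.6% to 2.7% and from 1.6% to 4.8%, so it stays below 5%. The plan names no test for this outcome; these rates only show scale.

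**The case against.** The strongest reply is that the researchers in item 4 may be the blinded panel. The monthly interval matches the months at which the primary is graded, and time to recovery could simply be read off those grades. The text does not exclude this. If it is what was meant, one sentence settles the matter; but the plan does not say so, and the change of term within the list points the other way.

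A reader might go further and infer that the plan has unblinded on-site staff judge this outcome at visits. The documents do not support that. Two sections state that research staff are blinded, no section places this judgement on site, and judgement at visits is only an inference from the monthly interval and the rule for ending therapy. What stands is narrower: a declared blind with no procedure to keep it.

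The routes to unblinding are also uneven. The diary route depends on which description of the control arm is right, and the tolerability route on which schedule is right. Neither is needed for the main point, since patients who know their arm still meet staff monthly.

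Finally, the panel's grading is itself incomplete: the plan gives no eFACES threshold for complete recovery and no rule for combining three raters. That is true, but the primary needs both anyway, so adopting its grades adds no further requirement.

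**Conclusion.** The point holds in a limited form. The plan does not link time to complete recovery to the blinded grades used for the primary, so the two recovery outcomes can disagree with no rule to settle it. The blind of the staff concerned is stated twice but not protected by the procedures. It does not follow that the assessment is planned to be unblinded, or that any bias will occur.

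The importance is modest. This is one of several secondary outcomes in a feasibility pilot, and the primary's grading is protected. The only size that follows directly from the plan is the weight of one patient, 6.7 points with 15 per arm or 5 points with about 20. Any larger figure rests on an assumed number or share of patients judged differently, for which the documents give no basis. The point is worth acting on because a better definition is available at almost no cost.

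**What to change.** - In Sections 4 and 8, define time to complete recovery as the first of months 1, 2 or 3 at which the blinded panel grades complete recovery, using the same photographs, definition and rater-combination rule as the primary.
- State that any recovery judgement made by study personnel during the study does not enter this outcome. Reconcile Section 4 (Duration of therapy and Outcome) with Section 8 on who declares recovery for analysis. No treatment rule needs to change for this.
- Reconcile Sections 4 and 6 on whether controls use a device, and Sections 4, 6 and 8 on when tolerability is asked and of whom, so that it is clear what follow-up staff can learn.

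The cost is wording. The primary already requires panel grades at all three months, so no extra visit, photograph or rating is needed. The rater-combination rule and the threshold for complete recovery still have to be written, but the primary needs them regardless.

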- 6. Patient reported treatment adherence through use of a diary and patient self-reporting at the three-month mark.
 - a. Diary of use which will be handed in monthly
 - b. Patient self-reported adherence using a Likert scale. The scale will have the following options for the patient to rate use: not at all, a little (1-2 week), rather regularly (3-5 week), very regularly (5 week on average), and as advised (daily).

Power calculations

When calculating the number of patients to be included in the pilot study, we wanted to have a realistic sample goal. This study is aimed at evaluating feasibility of recruitment and trial implementation. As mentioned earlier, our preliminary chart reviews show 350 patients were seen at OHSU for facial paralysis during 2014. We expect 15% of these patients are expected to meet the criteria for complete paralysis (n=53 patients) and additional patients will meet eligibility due to old age greater than 60 years. We believe we will be able to recruit the target number of 15 patients per group.

From this pilot trial we hope to gain more information on the effect size. Although adverse effects have not been documented in the prior clinical trials, clinicians in the community are still concerned about negative consequences of electrical stimulation that could have been missed by prior trials. In this trial we are aiming at including 15 patients per group for this pilot study, which would detect an adverse effect in 23% of the population with α for Type I error as 0.05 and power at 0.8.

9. Privacy, Confidentiality, and Data Security

Standard institutional practices will be followed as described in the OHSU Information Security and Research Data Resource Guide (http://ozone.ohsu.edu/cc/sec/isg/res_sec.pdf) to maintain the confidentiality and security of data collected in this study. Study staff will be trained with regard to these procedures. Paper files will be stored in locked filing cabinets in restricted access offices at OHSU. Electronic data is stored on restricted drives on the OHSU network. Electronic data will be stored on encrypted computers. Access to data/specimens is restricted to study personnel. Access to data requires OHSU ID/password authentication. Data from paper forms will be migrated to REDCap Database.

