Upon enrollment, subjects will be assigned a code that will be used instead of their name, medical record number or other personally identifying information. Electronic files for data analysis will contain only the subject code. Codes will not contain any part of the 18 HIPAA identifiers (initials, DOB, MRN) The key associating the codes and the subjects personally identifying information will be restricted to the PI and study staff. The key will be kept secure on a restricted OHSU network drive a in a limited access folder.

Cisco meeting which has been approved for use with PHI will be offered to participants who cannot make the visit. Best practices will be used with the cisco meeting telemedicine.

Three years after the study all data will be destroyed.

Data will not be shared with researchers outside of this study.

10. Provisions to Monitor the Data to Ensure the Safety of Subjects

We believe electric stimulation of the face for Bell's palsy offers a minimal risk. It is currently a therapy covered by many insurances for this indications. Five different clinical trials have not reported a negative impact of therapy (the references from these studies are in the risk and benefits section).

Confidentiality breech is a risk and the measures taken to prevent a problem are described above.

11. Risks and Benefits

a. Risks to Subjects

Our hope is to study if electric stimulation decreases these risks, but there is a potential that electric stimulation might worsen these complications.

This study also has the risk of being futile. Electric stimulation may not be effective in helping to treat your disease. This means subjects might spend time in the study and experience side effects that may not provide you with any health-related benefits.

Five published clinical trials have examined electrical stimulation of the face during acute Bell's palsy (Tuncay et al. 2015, Alakram et al. 2010, Manikandan et al. 2006, Flores et al. 1998 and Mosforth and Taverner 1958). Two trials reported mild benefit from electrical therapy (Tuncay et al. 2015 and Manikandan et al. 2006), while the rest showed no difference in recovery. Worse recovery with electrical stimulation has NOT been reported. However, some clinicians discourage electric stimulation because they are concern for worse outcomes based on patients they have treated and animal studied (mice studies) (Skouras et al 2009).

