Patients with Bell's palsy can experience residual weakness, facial spasms, inability to coordinate facial movements and unintentional facial movements (for example the eye can close when attempting to smile or the lip can twitch when closing the eye). Patients with Bell's palsy can experience pain and soreness on the side of the face that is paralyzed even if no electric stimulation is used. The complications from Bell's palsy happen even in patients who never receive electric stimulation.

Common side effects of electric stimulation are:

- -Mild to moderate discomfort during the 15 min of stimulation.
- -Skin redness from the stickers for the electrodes (NO needles are used)
- -You might experience skin irritation for the adhesive
- -You might experience worse soreness in the face

Investigational protocol for the device: There might be some side effects we do not expect because we are still learning about electric stimulation of the face. Effects of electric stimulation can take weeks to months to be noticeable. The FDA has approved the use of electric muscle stimulation.

Although it is highly unlikely the study will have an adverse effect on pregnancy given that it only affects the muscles being stimulated in the face. However, the following language was added to the consent to emphasize potential unknown risks. For pregnancy/risk to fetus (For Women): If you are nursing an infant or you are pregnant now, you can still participate in the study. Pregnant women have a higher risk of Bell's palsy than non-pregnant women and are suspected to have worse recovery than non pregnant women. (Reference: Petersen 2004 Bell's palsy: the spontaneous course of 2,500 peripheral facial nerve palsies of different etiologies. Acta Otolaryngol Suppl.) This study may involve risks not yet known to an embryo, fetus, or nursing infant that are currently unknown. If you are sexually active and could become pregnant, you and your partner(s) can consider using birth control. If you become pregnant during the research study, please tell the investigator and your doctor immediately.

Interviews/questionnaires/QOL assessments that discuss sensitive issues that may cause emotional upset: The questionnaires only revolve around facial paralysis and its consequences.

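### The claim that 15 per group detects a 23% adverse effect with 80% power states no event, control rate, test or sidedness, and the randomised comparison does not have that power

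*Combined protocol and SAP*

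**What the plan says.** Section 8, Power calculations, explains that the size was chosen as a realistic recruitment goal for a feasibility study. It then notes that clinicians worry about harms that earlier trials may have missed, and answers with the plan's only power statement: the trial aims for "15 patients per group for this pilot study, which would detect an adverse effect in 23% of the population", with alpha 0.05 and power 0.8.

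The rest of the protocol describes a two-arm comparison. Section 6 will "randomly assign study participants into either treatment or control groups with a 1:1 ratio". Section 8 says that results in the stimulated group "will be compared to results in the group that did not receive electric stimulation". The only test named in Section 8 is a rank sum test for House Brackmann scores.

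On harms, Section 11a says that "there is a potential that electric stimulation might worsen these complications", and also that "The complications from Bell's palsy happen even in patients who never receive electric stimulation". It adds that patients can have "pain and soreness on the side of the face that is paralyzed even if no electric stimulation is used". Section 4 describes the control as subsensory stimulation: "The settings will be the same as the intervention", with the voltage kept below what the patient can feel.

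**The concern.** A power statement for a binary event needs two rates (or one rate and a fixed reference), a test, and one or two sides. Here only one rate is given, and the text does not say whether it belongs to the treated arm, to all patients, or to a difference between arms. The event is not named.

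The sentence is offered as reassurance about missed harm. If the trial shows no significant excess of harm, a reader who trusts 80% power would take that as fair evidence against a harm of about 23%. If the real power is between a quarter and a half, the same result says little. The pilot is meant to inform a full-scale trial, so the misreading could carry forward.

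**Working it through.** **Inputs from the plan:** n = 15 per arm, 1:1, event rate 23%, alpha 0.05, target power 0.80 (Sections 6 and 8). **Assumed, because the plan does not give them:** control rate 0%, 5% or 10%; Fisher's exact test or the uncorrected chi-square; one or two sides.

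**1. Trying to reproduce the 80%.** The closest two-group match is the two-sided arcsine approximation against 0%:

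- h = 2·arcsin(√0.23) − 2·arcsin(√0) = 1.000
- power = Φ(h·√(15/2) − 1.96) = Φ(0.780) = 78%

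This may be the source of the figure. Against 5%, h = 0.549 and power = Φ(−0.456) = 32%. The approximation is unreliable at a rate of 0%: used as an actual test at this size, its true two-sided type I error reaches about 20%.

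**2. Exact power of the between-group comparison.** Power = Σ P(X = a)·P(Y = b) over all outcomes (a, b) that reject in the harmful direction, with X ~ Bin(15, 0.23) and Y ~ Bin(15, control rate). With 0% in controls, Y is always 0 and power is P(X ≥ r), where r is the smallest treated count that rejects against 0/15:

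- two-sided Fisher, r = 5: 25.0%
- one-sided Fisher and two-sided chi-square, r = 4: 46.5%
- one-sided chi-square, r = 3: 70.6%

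| Test | Power vs 0% | vs 5% | vs 10% | Rate for 80% power vs 0% | vs 5% | vs 10% |
|---|---|---|---|---|---|---|
| Fisher, two-sided | 25.0% | 13.0% | 6.5% | 40.8% | 53.7% | 63.4% |
| Fisher, one-sided | 46.5% | 25.6% | 13.6% | 33.7% | 47.0% | 57.0% |
| Chi-square, two-sided | 46.5% | 26.0% | 14.3% | 33.7% | 45.4% | 54.3% |
| Chi-square, one-sided | 70.6% | 43.3% | 26.1% | 26.4% | 38.5% | 47.7% |

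Maximum type I error over all common rates is 1.8% and 2.2% for the two Fisher tests, and 5.5% and 5.9% for the two chi-square tests. The chi-square figures are therefore slightly flattered.

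**3. Reading 23% as a difference.** For 28% against 5%, the most lenient of these tests (one-sided chi-square) has 57% power. This reading does not reach 80% either.

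**4. Reading it as a one-arm test.** Exact binomial, one-sided 0.05, n = 15:

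- Background at most 2.42%: reject at 2 or more events; power at 23% is 89.1%.
- Background 5%: reject at 3 or more; 70.6%.
- Background 10%: reject at 5 or more; 25.0%.

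**5. Is a near-zero background plausible?** Not for the harms that matter most here. Section 11a says that palsy complications and soreness occur without stimulation. Section 4 puts complete recovery at 61% in complete paralysis, which leaves 100 − 61 = 39% without it, and at one-third in patients over 60. Under the subsensory control in Section 4, redness from the electrodes can occur in controls too.

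**The case against.** The strongest reply is that the figure is under-specified and not proven to be miscalculated. The sentence gives one rate and no comparator, and the clause before it says that earlier trials documented no adverse effects, so the authors may have had a near-zero background in mind. On that view the arcsine result (78%) or the one-arm result (89%) is close enough. This stands in part: some method does come near 80%. But each route needs an assumption that the plan does not state, and Section 11a contradicts that assumption for worsened palsy complications and soreness.

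A second reply concerns the control arm. Section 6 says that half the patients receive no stimulation, which conflicts with the subsensory control in Section 4. If controls wear no electrodes, discomfort during stimulation, electrode redness and adhesive irritation would be 0% in controls by design. That is fair for those three effects. Even so, at 0% none of the four between-group tests reaches 80%.

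Third, Section 2 gives 40 patients and Section 6 about 20 per treatment. At 20 per arm, power against 0% runs from 50% (two-sided Fisher) to 87% (one-sided chi-square), and against 5% from 24% to 54%. The power sentence itself says 15, so this does not rescue it, but any replacement figure must use the final size.

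Finally, no test of adverse events is planned and no decision depends on the sentence. That limits the consequence to how a null safety result is read.

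**Conclusion.** The concern holds. The statement cannot be verified as written. On the reading that fits the randomised design, power for a 23% adverse effect is 25% to 71% with no events in controls and 13% to 43% with 5% in controls, depending on the test, against the stated 80%. The rate detectable with 80% power is 26% to 41% against 0%, and 39% to 54% against 5%. The control rates, tests and sidedness are assumptions, and other methods would give other figures. The 0% case is the most favourable control rate. The sample size rests on feasibility and is not called into question; the power claim needs correcting.

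**What to change.** Keep the sample size. Name the event (worse recovery or synkinesis, or the listed side effects in Section 11a) and replace the sentence in one of two ways.

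1. **Precision statement.** With 15 treated patients, the chance of seeing at least one event is 1 − 0.90^15 = 79% if the true rate is 10%, and 1 − 0.82^15 = 95% if it is 18%. If none of 15 has the event, the exact two-sided 95% upper limit is 1 − 0.025^(1/15) = 22%. For events that also occur in controls, add the Newcombe 95% interval for the difference between arms: about ±28 points at 3/15 in each arm and ±32 at 6/15. For rarer events, 1/15 or 2/15 in each arm, it is about ±24 or ±26.
2. **Detectable rate with its test and a range of control rates.** 80% power at about 41%, 54% and 63% against 0%, 5% and 10% (two-sided Fisher), or 34%, 45% and 54% (two-sided chi-square, noting that it slightly exceeds alpha).

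Either way, report adverse event rates by arm with exact confidence intervals, and recompute these figures if the final size is not 15 per arm.

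A side item: Section 6 says "if you are in the electric stimulation we will ask about tolerability and satisfaction", while the tolerability outcome in Sections 4 and 8 has no arm restriction. State which arms complete that form, because a between-arm comparison needs both.

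The cost is protocol wording and that one clarification. The stated figure becomes less favourable; no patients or visits are added.
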